## ***Data Analysis***

The current study is a 2-week, 4-arm dose-escalation trial to determine the safety/tolerability and PK of pravastatin when co-administered with the standard drug regimen for drug-susceptible TB (Rifafour). Participants will receive standard anti-TB therapy and pravastatin beginning at a dose of 40 mg once daily. Each subsequent arm (pravastatin 80 mg, 120 mg, and 160 mg) of this study will continue to recruit participants until at least 10 participants in each group are evaluable for full PK analysis.

The primary endpoints in this study are safety/tolerability and pravastatin exposures. A regimen will be deemed safe and well tolerated if none of the participants require treatment discontinuation for a pravastatin-related adverse reaction and  $\leq 3$  participants experience a pravastatin-related grade 3 (or higher) adverse event during the 14-day study period and follow up. PK parameters (e.g., area under the concentration-time curve over 24 hours ( $AUC_{0-24}$ ), minimum concentration ( $C_{min}$ ), maximum concentration ( $C_{max}$ ), and oral clearance (Cl/F)), will be estimated for pravastatin from intensive sampling data after a single dose of pravastatin (baseline PK, prior to initiation of TB treatment) and after 14 days of co-administration with the first-line anti-TB regimen. Based on PK data of pravastatin when co-administered with rifampin ( $T_{max} = 1$  hour,  $T_{1/2} = 1.5$  hours), plasma samples will be collected for pravastatin measurements by LC-MS/MS at the following time points: pre-dose, 0.5 hrs, 1 hr, 1.5 hrs, 2 hrs, 3 hrs, 4 hrs, 6 hrs, and 8 hrs. Pravastatin exposures will be calculated using a noncompartmental approach using standard PK software, e.g., Phoenix WinNonLin. Using all PK data, a PK/PD model will be developed to evaluate the relationship between drug exposures (e.g.,  $C_{max}$ ,  $T_{max}$  or  $AUC_{0-24}$ ) and outcomes (e.g., safety/tolerability).  $C_{max}$  and  $t_{max}$  will be taken directly from the original data. The terminal log-linear phase of the plasma concentration-time curve will be identified visually for each curve.

The elimination rate constant ( $k_e$ ) will be determined by a linear regression analysis using the last 3–8 points on the plot of the natural logarithm of the plasma concentration-time curve. The  $t_{1/2}$  value will be calculated from the equation  $t_{1/2} = \ln 2/k_e$ . AUC values will be calculated by the linear trapezoidal rule for the rising phase and the log-linear trapezoidal rule for the descending phase, with extrapolation to infinity, when appropriate, by dividing the last measured concentration by  $k_e$ . Results will be expressed as mean values ( $\pm$  s.d.). 95% confidence intervals will be calculated for the mean differences between the baseline pravastatin and rifampin co-administration phases for  $AUC(0-\infty)$ ,  $C_{max}$  and  $t_{1/2}$ . Statistical comparisons of the pharmacokinetic variables (except  $t_{max}$ ) will be carried out by the Student t-test for paired values (two-tailed), and the Wilcoxon signed-rank test will be used for analysis of  $t_{max}$ . Logarithmic transformation of  $C_{max}$  and AUC values will be done prior to statistical analysis. The effect of rifampin (and other anti-TB drugs) on the  $AUC(0-\infty)$  of pravastatin will be assessed with a t-test of log-transformed values. The analysis will be performed with Systat for Windows, V6.0.1 (SPSS Inc., Chicago, Ill). Statistical significance will be taken as  $P < 0.05$ .

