### ***Safety and Tolerability Endpoints***

The primary endpoint for analysis of safety and tolerability is Grade 3 or higher adverse events. Secondary endpoints include permanent discontinuation of assigned study regimen for any reason (other than new recognition of participant ineligibility based on absence of *M. tuberculosis* growth in baseline sputum cultures, or growth of *M. tuberculosis* resistant to rifampin by GeneXpert. Other aspects of safety and tolerability that will be assessed include mortality and the rates and types of toxicity thought related to study drugs by the Investigator.

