***Secondary outcome variables***

Steady-state PK of pravastatin among patients with pulmonary TB receiving co-administered Rifafour (isoniazid, rifampin, pyrazinamide and ethambutol)

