### ***Decision-making algorithm for pravastatin safety/PK study:***

Scenario/Pravastatin Dose	Safe/tolerable?	<math>AUC_{0-24}</math> reduction	Decision
1 40 mg daily	Y	=	Increase dose to prava 80 mg and enroll additional participants
2 40 mg daily	N	=	Enroll 5 additional participants (10 total) and discontinue study

3 80 mg daily	N	=	Discontinue study
4 80 mg daily	Y	< 40%	Discontinue study
5 80 mg daily	Y	≥ 40%	Increase dose to prava 120 mg and enroll additional participants
6 120 mg daily	N	=	Discontinue study
7 120 mg daily	Y	<40%	Discontinue study
8 120 mg daily	Y	≥ 40%	Increase dose to prava 160 mg and enroll additional participants
9 160 mg daily	N	=	Discontinue study
10 160 mg daily	Y	=	Study complete

Safety/tolerability: Y= Yes; <3 participants with  $\geq$  one grade 3 (or higher) event of musculoskeletal symptoms, creatine kinase elevation, or liver function test elevation attributed to study drug (probable or definite)

N= No; For Arm 1 (pravastatin 40 mg daily):  $\geq$  1 participant with  $\geq$  one grade 3 (or higher) event of musculoskeletal symptoms, creatine kinase elevation, or liver function test elevation attributed to study statin medication (probable or definite).

For Arms 2, 3, and 4:  $\geq$  3 participants with  $\geq$  one grade 3 (or higher) event of musculoskeletal symptoms, creatine kinase elevation, or liver function test elevation attributed to study statin medication (probable or definite)

$AUC_{0-24}$ = Area-under-the-plasma-concentration-time curve for 24-hour exposure

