#### ***Decision-making algorithm for initiating new dosing cohorts***

The study will be monitored by a DSMB, which will review the safety data for each cohort and will give approval before initiation of each possible dose escalation. Specifically, study drug dose will not be escalated and the study if any three participants develop grade 3 or higher musculoskeletal/CK-related adverse events (AEs), LFT-related AEs ( $> 5 \times UNL$  without symptoms, but  $> 3 \times UNL$  with symptoms or bilirubin  $> 2 \times ULN$ ) or any type of grade 4 event regardless of causal attribution. Study drug dosage will be escalated only if the dose is deemed safe/tolerable based on the above rules and the mean pravastatin AUC is reduced by  $\geq 40\%$  relative to the pre-Rifafour value. Study participants in whom the study drug has been discontinued will remain in the study until the final clinical visit and laboratory evaluation. In the event of study product discontinuation, management of the standard-of-care TB drugs will revert to the site clinician as per national guidelines.

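### Section 18 reaches a safety verdict from event counts but plans no proportion or interval for the primary safety endpoint, and its count rules disagree

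*Combined protocol and SAP*

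**What the plan says.** **Endpoint.** Section 4 (Safety and Tolerability Endpoints): "The primary endpoint for analysis of safety and tolerability is Grade 3 or higher adverse events". It also says that the frequency and kinds of drug-attributed toxicity will be assessed, without giving a method.

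**Safety verdict.** Section 18 (Data Analysis) joins two conditions with *and*. The first is "A regimen will be deemed safe and well tolerated if none of the participants require treatment discontinuation for a pravastatin-related adverse reaction". The second is that no more than three "participants experience a pravastatin-related grade 3 (or higher) adverse event during the 14-day study period and follow up".

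**Decision table.** The footnote to the decision-making algorithm for the safety/PK study uses another rule: "Safety/tolerability: Y= Yes; <3 participants with" a grade 3 or higher musculoskeletal, CK or liver-test event rated probably or definitely due to study drug. Arms 2 to 4 fail at three or more such participants, and Arm 1 fails at one.

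**Escalation rule.** The algorithm for initiating new dosing cohorts blocks escalation if any three participants have the listed grade 3 or higher events "or any type of grade 4 event regardless of causal attribution". DSMB approval is needed before each escalation.

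**Sample size.** Ten evaluable participants per arm (five in Arm 1) are justified by the precision of the pravastatin AUC ratio. The only intervals in section 18 are for PK.

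**Hierarchy.** Data Analysis: "The primary endpoints in this study are safety/tolerability and pravastatin exposures". Section 17 lists PK as a secondary outcome: "Steady-state PK of pravastatin among patients with pulmonary TB receiving co-administered Rifafour".

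**The concern.** A count can serve as a go/no-go rule for opening the next cohort. Here it is also the trial's stated conclusion on its primary safety endpoint, and section 2 says that the findings will inform the dose for a larger study. A pass from 10 participants leaves a wide range of true event rates open, and nothing in the planned output would show that range.

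The denominator is also open. Section 9 replaces participants who stop after one or more doses of pravastatin, while section 18 counts evaluable participants. Without a stated all-dosed population, someone who stopped for toxicity could drop out of the safety summary.

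Finally, if section 17 governs, the only primary outcome has no precision statement at all.

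**Working it through.** **1. The plan's own figure.** Inputs from Sample size: within-subject CV 33%, n = 10, 90% interval on the log scale. Half-width = t(0.95; 9 df) × √ln(1 + 0.33²) × √(2/10) = 1.833 × 0.3215 × 0.4472 = 0.264, which agrees with the stated 26%. (The printed interval of 0.74 to 1.35 needs a half-width of 0.30; 0.264 gives 0.77 to 1.30.) There is no matching figure for safety.

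**2. Decision-table rule.** Let p be the true probability that a participant has a counted event. The documents give no value, so p = 10%, 20% and 30% are assumptions. Participants are taken as independent, with exactly 10 counted (5 in Arm 1).
- Arms 2 to 4 at p = 20%: P(X ≤ 2) = 0.8¹⁰ + 10(0.2)(0.8⁹) + 45(0.2²)(0.8⁸) = 0.107 + 0.268 + 0.302 = 0.678.
- Arm 1 at p = 20%: P(X = 0) = 0.8⁵ = 0.328.

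**3. Data Analysis rule.** Let d be the chance that a grade 3 or higher event leads to discontinuation. P(pass) = Σ(x = 0 to 3) C(10,x) pˣ(1−p)¹⁰⁻ˣ(1−d)ˣ. At p = 20%:
- d = 0: 87.9%
- d = 0.25: 56.4%
- d = 0.5: 34.2%
- d = 0.75: 19.7%
- d = 1: 10.7%

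Section 5 requires stopping for the ALT criteria, for grade 3 or higher CK, and for listed grade 3 toxicities judged due to study drug. So d = 0 is an extreme. The formula counts only discontinuations that follow a grade 3 or higher event. Section 5 also requires stopping at ALT above 3 × ULN with symptoms, which can be grade 2 in the grading table (2.5 to below 5 × ULN). Such stops would lower the pass probability further.

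| True rate | Arms 2–4, fewer than 3 of 10 | Arm 1, 0 of 5 | Data Analysis rule, n = 10 (d = 1 to d = 0) |
|---|---|---|---|
| 10% | 93.0% | 59.0% | 34.9–98.7% |
| 20% | 67.8% | 32.8% | 10.7–87.9% |
| 30% | 38.3% | 16.8% | 2.8–65.0% |

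**4. What an interval would show.** Exact (Clopper-Pearson) 95% limits:
- 0/5: 0–52%
- 0/10: 0–31% (upper limit 1 − 0.025^(1/10) = 0.308)
- 1/10: 0.3–45%
- 2/10: 2.5–56%
- 3/10: 6.7–65%

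**5. The rules side by side.**
- *Three counted events in 10, no discontinuation:* passes Data Analysis, fails the decision table in Arms 2 to 4, and blocks escalation under the cohort algorithm.
- *One or two counted events in 10, with a discontinuation judged pravastatin-related:* fails Data Analysis but is a Y in the decision table. If every counted event led to stopping, then at p = 20% this would happen with probability 67.8% − 10.7% = 57%.
- *Arm 1 with one or two events:* meets both the general Y (fewer than three) and the Arm 1 N (one or more).
- *Attribution:* the decision table uses probable or definite, the relatedness table in section 5 has only related and not related, and the cohort algorithm counts grade 4 events whatever their cause.

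**The case against.** The other side has good points. This is a small dose-escalation study, and 10 per arm is not in itself a fault. A DSMB must approve each escalation and also considers early stopping. Section 4 mentions the frequency of drug-attributed toxicity, and Data Analysis plans a model relating exposure to safety. So it would be wrong to say that safety rests on one count with no other scrutiny. None of this supplies an estimator, a denominator or an interval for the primary safety endpoint.

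A reader might infer that the plan passes a dose with a 20% severe-event rate up to 88% of the time. The documents do not support that as a description of the Data Analysis rule. The 88% holds only if no counted event leads to discontinuation, whereas that rule allows no pravastatin-related discontinuation and section 5 makes stopping mandatory for many such events. Depending on d, the rule may be lax or strict. Nor does the 68% extend to Arm 1, where the figure is 33%.

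The 20% is an assumption, and each rule counts a different set of events. The one related figure in the documents, CK above 10 × ULN in 4 of 464 patients (0.9%) on 80 mg (section 13, Pravastatin, Tolerability), covers one event type and is not a rate for this combination. Section 15 calls the effect of adding the other TB drugs unknown.

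**Conclusion.** The point stands in this form. Section 18 gives a safety verdict without a proportion or interval for the primary safety endpoint, sizes the trial on PK only, and does not define who is in the safety denominator. At an assumed 20% rate of the counted events, the pass probability is 68% for Arms 2 to 4 under the decision table, 33% for Arm 1, and 11–88% under the full Data Analysis rule. The figures assume independent participants and fixed counts of 10 and 5. Replacement could make the number treated larger. The 11% also assumes that nobody stops for a pravastatin-related reaction below grade 3.

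The intervals do not depend on the assumed rate: no events in 10 still leaves a true rate of up to 31% open. This does not show that any dose is unsafe or that either threshold is wrong. It shows that the planned conclusion is firmer than the data can support. The disagreement over whether PK is primary or secondary is a labelling fault. It matters because it decides whether any precision statement covers the primary outcome.

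**What to change.** (a) In section 18, report the grade 3 or higher endpoint per arm and pooled as a proportion with an exact Clopper-Pearson 95% interval. The denominator should be all participants who took at least one dose of pravastatin, including those later replaced. Base the reported safety conclusion on the estimate and interval, not on the pass/fail count alone.

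(b) Reconcile the rules in Data Analysis, the decision table and the cohort algorithm on three events in 10, discontinuations, attribution and Arm 1. Which threshold applies is for the sponsor and the DSMB; this review does not choose one.

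(c) Make section 17 and Data Analysis agree on whether PK is primary or secondary.

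If pass probabilities are printed, compute them for the reconciled rule, including any discontinuation condition, over a range of true rates, with Arm 1 shown separately.

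Cost: SAP wording and one table, with no extra participants or procedures. The safety statement will read less favourably.

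### Section 18 gives three different tests of whether a dose is safe and tolerable and does not say which one governs, so the same cohort can pass one and fail another

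*Combined protocol and SAP*

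**What the plan says.** All three tests are in Section 18.

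- **Data Analysis.** "A regimen will be deemed safe and well tolerated if none of the participants require treatment discontinuation for a pravastatin-related adverse reaction", and if no more than three "participants experience a pravastatin-related grade 3 (or higher) adverse event during the 14-day study period and follow up". Any type of event counts, and the limits are the same in every arm.
- **Decision-making algorithm for pravastatin safety/PK study (the decision table).** "Safety/tolerability: Y= Yes; <3 participants with" at least one listed grade 3 or higher event, with no arm named. No is reached at one participant in Arm 1 and at three in Arms 2-4. What counts is an "event of musculoskeletal symptoms, creatine kinase elevation, or liver function test elevation attributed to study statin medication (probable or definite"). Discontinuation is not a criterion.
- **Decision-making algorithm for initiating new dosing cohorts (the cohort-initiation rule).** There is no escalation "if any three participants develop grade 3 or higher musculoskeletal/CK-related adverse events", liver-test events with their own cut-offs (above 5 x ULN without symptoms, above 3 x ULN "with symptoms or bilirubin" above 2 x ULN), "or any type of grade 4 event regardless of causal attribution". It has no separate Arm 1 limit. It then adds: "Study drug dosage will be escalated only if the dose is deemed safe/tolerable based on the above rules" and the mean AUC has fallen by at least 40%.

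Section 5 matters in two ways. Under Creatinine Kinase Elevation, a grade 3 or higher rise means permanent discontinuation of the statin. Under Relationship of AE to Study, and in the attribution table, causality has two levels, Related and Not Related.

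**The concern.** Safety/tolerability is a primary endpoint, and the same verdict decides whether the next cohort receives 120 or 160 mg. The three tests differ in count, in whether a discontinuation matters, in the events counted and in the attribution required. The decision table also asks for a probable or definite rating, which the two-level scale cannot supply. The lead sentence above the attribution table treats a possible attribution as association, and the decision table leaves that level out. If the governing test is chosen after a cohort's data are known, the primary verdict and the escalation decision depend on that choice.

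**Working it through.** The plan gives no error rate or operating characteristic for these tests, so there is no figure to reproduce.

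**Step 1. Apply the three tests as written. No event rate is needed.**

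| Cohort | Data Analysis | Decision table | Cohort-initiation rule |
|---|---|---|---|
| Arms 2-4: one grade 3 CK rise on treatment, attributed to pravastatin (stop mandatory) | Fail | Yes | Not blocked |
| Arms 2-4: three grade 3 musculoskeletal, CK or liver-test events, probable or definite, first found at Day 21 or 30 (last dose Day 15, so no stop possible) | Pass | No | Blocked |
| Arms 2-4: three unrelated grade 4 events, none of the other criteria met | Pass | Yes | Blocked |
| Arm 1: one qualifying event found after the last dose | Pass | Yes (<3) and No (≥1) | Not blocked |

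**Step 2. How often would Data Analysis and the decision table disagree in a cohort of 10?**

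Inputs:
- Ten evaluable participants per cohort in Arms 2-4 (Section 18, Sample size).
- Participants who stop early are replaced (Section 9).
- The only document-based event rate is CK above 10 x ULN in 4/464 = 0.86% at 80 mg (Section 13, Pravastatin, Tolerability). The exact 95% interval is 0.24% to 2.19%. This is CK only, over a mean of 8.6 months and not from this 14-day combination setting.
- Rates of 5% and 10% are assumptions.
- The share f of events that force a stop is an assumption, taken from 0.25 to 1. The value 0.25 would hold if events were equally likely to be found at each of the four scheduled draws (Days 7, 15, 21, 30), since only Day 7 precedes further doses. Daily adverse-event assessment could make it higher.

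Model: each dosed participant has a counted event with probability p, and q = pf. The number of stops before 10 are evaluable has P(s) = C(9+s, s) q^s (1−q)^10. Non-stop events among the 10 are e ~ Binomial(10, p(1−f)/(1−q)).

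- A (Data Analysis fails, decision table Yes) = P(s ≥ 1 and s + e ≤ 2). This is the discontinuation clause.
- B (Data Analysis passes, decision table No) = P(s = 0, e = 3). This is the ≤3 versus <3 count.

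Worked case, p = 0.05, f = 1: A = 10(0.05)(0.95)^10 + 55(0.05)²(0.95)^10 = 0.299 + 0.082 = 0.382, and B = 0.

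Worked case, p = 0.05, f = 0.25: q = 0.0125, (1−q)^10 = 0.882, and the non-stop probability is 0.0375/0.9875 = 0.0380. B = 0.882 × P(e = 3) = 0.004, and A = 0.110.

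| p | A + B at f = 0.25 / 0.50 / 1 | Largest B over these f |
|---|---|---|
| 0.86% | 0.02 / 0.04 / 0.08 | 0.00003 |
| 2.19% | 0.05 / 0.10 / 0.20 | 0.0005 |
| 5% (assumed) | 0.11 / 0.21 / 0.38 | 0.004 |
| 10% (assumed) | 0.20 / 0.33 / 0.54 | 0.024 |

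If no event forced a stop (f = 0), A would vanish and B would be 0.010 at 5% and 0.057 at 10%. The model lets both tests count the same events, so it leaves out splits caused by the different event lists.

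**Step 3. Effect of the discontinuation clause alone.** P(at least one forced stop) = 1 − (1 − pf)^10. For f from 0.25 to 1 this is 0.02-0.08 at 0.86%, 0.12-0.40 at 5% and 0.22-0.65 at 10%.

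**The case against.** The best reply is that the tests have different jobs. Data Analysis would give the final verdict, and the two algorithms would control escalation. The headings suggest this, but no text says it. Even on that reading, a dose could clear escalation and then fail the primary endpoint on one event.

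A second reply is that the cohort-initiation rule refers to its preceding rules in the plural and needs monitoring-board approval, so the natural reading is that every rule must be met. That is possible, and it is the cautious reading. The plan does not state it, and it would not resolve Arm 1, where the decision table contradicts itself.

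A third reply concerns harm. Individual stopping rules in Section 5 apply whichever cohort test governs. Escalation also requires a mean AUC fall of at least 40%. With dose proportionality and the same fall, 120 mg gives at most 120 × 0.6 = 72 mg-equivalent mean exposure. For 160 mg the figure is 96 at a 40% fall and 80 at the 50% fall behind the expectation in Section 15. This stands for mean exposure, but the plan itself notes that the rifampin effect varies greatly between subjects.

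A reader might also infer more than the documents support:

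- **That any three related grade 3 events split the tests.** They do so only if they are musculoskeletal, CK or liver-test events. Three related grade 3 rashes with no stop pass all three.
- **That the single CK example applies in every arm.** In Arm 1 one attributed event also reaches the decision table's No, so the example is clean only in Arms 2-4.
- **That three symptomatic ALT rises of 4 x ULN (grade 2) block escalation.** This depends on whether the grade 3 qualifier in the cohort-initiation rule also governs its liver-test item, which is unclear.
- **That attribution by product is missing.** Relationship of AE to Study already says pravastatin and Rifafour will be assessed. What is missing is a probable/definite level, and the attribution table pools the two products under Related.

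**Conclusion.** The conflict is confirmed from the text. The cohorts in Step 1 need no assumed rate, and no provision says which test governs.

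The discontinuation clause is the main source of disagreement between Data Analysis and the decision table, and there Data Analysis is the stricter test. The ≤3 versus <3 mismatch is a real drafting error but adds little: at most 0.004 at 5% and 0.024 at 10% for f of 0.25 or more.

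The probabilities should not be read as forecasts. Every f, and both the 5% and 10% rates, are assumptions, and the 0.86% comes from a different setting. Nor do the documents show that participants would go unprotected. The finding is that the primary safety verdict and the escalation decision are not uniquely defined.

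**What to change.** Amend Section 18 before the next cohort review.

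1. Make the decision table the single governing rule, and have Data Analysis and the cohort-initiation rule refer to it.
2. In Arms 2-4, No at three or more participants, replacing the limit of up to three in Data Analysis, and Yes below three. In Arm 1, No at one or more and Yes only at zero.
3. Keep the discontinuation clause in the governing rule by default, because it is the stricter stated criterion. Deleting it is a trade-off for the sponsor to settle before the review, since it is the only criterion by which one event fails Arms 2-4.
4. Carry over the cohort-initiation list. Apply the any-cause wording to grade 4 events only, and use the liver-test cut-offs as written, not limited to grade 3.
5. Replace the probable/definite level with Related to pravastatin, rated separately from Rifafour.

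The cost is an amendment, with no new data or participants, but escalation becomes harder than under the decision table alone. With the clause kept, a 10-participant cohort fails on at least one forced stop with the Step 3 probabilities, and in Arms 2-4 a No ends the study. In Arm 1, one Related liver-test event on hepatotoxic TB drugs would end escalation, and Related is a lower bar than probable or definite.

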**18. Statistical Analysis Plan**

***Hypothesis***

Pravastatin given at the standard clinically recommended dose will be safe and well tolerated, and pravastatin drug exposures will not be significantly altered following co-administration with rifampin in the 14-day study.

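### The SAP states log transformation for AUC but not for Cl/F, its reciprocal at fixed dose, and does not label or align its lead PK contrast

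*Combined protocol and SAP*

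**What the plan says.** The Hypothesis in section 18 is that "pravastatin drug exposures will not be significantly altered following co-administration with rifampin in the 14-day study". It names no PK variable.

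Data Analysis states that "The primary endpoints in this study are safety/tolerability and pravastatin exposures". It gives an open list of parameters (AUC0-24, Cmin, Cmax, "and oral clearance (Cl/F)), will be estimated for pravastatin from intensive sampling data") from the Day 1 and Day 15 profiles. Section 17 instead places PK under secondary outcome variables: "Steady-state PK of pravastatin among patients with pulmonary TB receiving co-administered Rifafour".

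For inference, Data Analysis says that comparisons of the PK variables other than tmax "will be carried out by the Student t-test for paired values (two-tailed"), and that "the Wilcoxon signed-rank test will be used for analysis of" tmax. On scale it says "Logarithmic transformation of $C_{max}$ and AUC values will be done prior to statistical analysis". Cl/F, Cmin and t1/2 are not mentioned there. A separate sentence assigns the effect of rifampin on AUC(0-∞) to a t-test of log values. Confidence intervals are promised for AUC(0-∞), Cmax and t1/2. The threshold covers everything: "Statistical significance will be taken as $P < 0.05". No multiplicity rule is given, and no variable is labelled as the lead or as supportive.

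The decision table works on AUC0-24, and the text on initiating new cohorts on mean AUC. Both use a reduction of at least 40%, without a P value.

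**The concern.** With the same dose on both days, Cl/F carries no information beyond AUC. On the log scale, a paired test of Cl/F is the AUC test with its sign reversed. On the raw scale it becomes a different test, weighted towards participants with the highest clearance. The report could then show a significant fall in AUC beside a non-significant change in Cl/F, from the same samples.

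This matters more than usual because the hypothesis is worded as exposures not being significantly altered, so a non-significant result can be read as support for it. The Objectives say the findings will inform dose selection for the follow-up study. The reader also has to work out which AUC answers the question, and whether PK is a primary or a secondary outcome.

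**Working it through.** **Inputs from the documents.** n = 10 per arm in Arms 2 to 4, and 5 in Arm 1; within-subject CV 33%, range 6-60% (Sample size). Between-subject CV of AUC 50-60% (section 13, Pravastatin, Pharmacokinetics). Expected AUC reduction 30-50% (section 13, Drug-drug interactions). Two-sided 0.05 (Data Analysis).

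**Assumptions not in the documents.** Log-normal AUC and equal within-subject variance on both days. A between-subject CV of 55% is used as the midpoint of the stated range.

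**The plan's own figure.** The log-scale within-subject SD is sqrt(ln(1 + 0.33²)) = 0.3215. The standard error of the mean paired log difference is 0.3215 × sqrt(2/10) = 0.1438. The half width of the 90% interval is t(0.95, 9 df) × 0.1438 = 1.833 × 0.1438 = 0.264. This reproduces the stated 26% and confirms that the planned design is a paired log-AUC comparison. (Back-transformed, 0.264 gives 0.77 to 1.30 rather than the printed 0.74 to 1.35. That is a separate matter.)

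**The identity.** Cl/F = dose/AUC, so log Cl/F = log dose − log AUC. With dose constant, the Day 15 minus Day 1 difference in log Cl/F is the negative of the difference in log AUC, and the two-sided P values are equal. In simulation, the logged versions disagreed in no cohort.

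**Log AUC, direct check.** At a 30% reduction the noncentrality is |ln 0.7| / 0.1438 = 0.3567 / 0.1438 = 2.48. With 9 df this gives power of about 60%, matching the simulation.

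**Log AUC against raw Cl/F, simulated (n = 10, within-subject CV 33%, between-subject CV 55%).**

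| True reduction | Log AUC significant | Raw Cl/F significant | Verdicts differ |
|---|---|---|---|
| 30% | 60% | 48% | 17% |
| 40% | 88% | 76% | 14% |
| 50% | 99% | 93% | 6% |

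**Sensitivity.** Over between-subject CV 50-60%, the verdicts differ in 16-19%, 13-16% and 5-7% of cohorts at the three reductions. With within-subject CV 60%, the top of the plan's range, they differ in 12-24%. With n = 5 (Arm 1) and CV 33%, they differ in 12-29%. With no true change they differ in about 3%.

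**Direction.** At a 30% reduction, AUC alone is significant in 13.5-16.2% of cohorts and Cl/F alone in about 2.5%. The extra test therefore mostly adds a non-significant result where AUC shows a fall.

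**Multiplicity.** Data Analysis ties four variables by name to an interval or a test: AUC(0-∞), Cmax, t1/2 and tmax. If nothing changed, the chance of at least one P < 0.05 in one arm is 1 − 0.95⁴ = 0.19 if they are independent, 0.16 at correlation 0.5 and 0.12 at 0.8. The correlation is assumed, and tmax is treated as a t-test. Adding raw Cl/F to log AUC raises the false-positive rate only from 5.0% to about 6%, because the two differences correlate at about −0.85.

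**Which AUC.** The test sentence uses AUC(0-∞) and the decision table uses AUC0-24. With the half-life of 1.5 hours given in Data Analysis, 24 hours is 16 half-lives, and 0.5¹⁶ is about 0.000015. Assuming mono-exponential decline, the two areas should nearly coincide, so this is a labelling mismatch more than a numerical one.

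**The case against.** The strongest reply is that the plan already treats AUC as the lead. The precision statement is for AUC, escalation is on AUC, and one sentence assigns the rifampin effect to a t-test of log AUC(0-∞). That stands: a reader might infer that the SAP has no lead contrast at all, and the documents do not support this. What is missing is the label, agreement on which AUC, and agreement on whether PK is primary or secondary.

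Second, the plan nowhere states that Cl/F will be tested raw. Cl/F appears in an open list of parameters to be estimated, and the tests section does not name it. This also stands. Raw testing follows from the general t-test clause together with a transformation sentence limited to Cmax and AUC. It is the natural reading, not a stated rule.

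Third, a reader might infer serious inflation of a primary-endpoint error rate over six or more tests. The documents do not support that. Six tests requires counting AUC and Cl/F as separate variables when one determines the other. The status of PK is itself inconsistent. A scenario with no change in any variable is not what the plan expects, since it anticipates a 30-50% fall.

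Fourth, near the roughly 50% reduction cited in the rationale for escalating up to 160 mg, disagreement is only about 6%. That is correct. The larger figures belong to the lower part of the expected range or to higher variability.

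**Conclusion.** The point holds as a gap in specification with a modest, quantifiable effect on reporting. On the natural reading, Cl/F gives a second, weaker test of the AUC interaction, and its verdict differs from that of log AUC in about 17%, 14% and 6% of 10-person cohorts at true reductions of 30%, 40% and 50%. These figures rest on log-normal AUC, equal within-subject variance on both days, the plan's 33% within-subject CV and a 55% between-subject CV.

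The lead contrast is recognisable but unlabelled, and its definition differs between the test sentence and the decision table. The multiplicity figure is secondary: 0.12-0.19 in one arm for the four named variables, dependent on the assumed correlation.

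A reader might infer that dose escalation is at risk. It is not, because escalation depends on safety and the AUC point estimate against 40%, and no decision rule uses these P values. Nor do the documents tie the follow-up dose to a P value for Cl/F, t1/2 or tmax. What is affected is the reported conclusion about the interaction.

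**What to change.** In Data Analysis:

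1. State that AUC, Cmax and Cl/F, and also Cmin and t1/2 where values are positive, are log-transformed and reported as geometric mean ratios (Day 15 to Day 1) with confidence intervals. The qualification is needed for Cmin because the Day 1 pre-dose value should be zero and the trough may be unmeasurable.
2. Name one paired log-AUC ratio as the lead PK contrast. AUC0-24 would match the decision table. Amend the AUC(0-∞) sentence to agree, so that the section does not carry two competing lead tests.
3. Report the remaining PK variables, including tmax, as supportive estimates with intervals and without significance claims.
4. Make section 17 and Data Analysis agree on whether PK is a primary or a secondary outcome.

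The cost is SAP wording only, with no extra participants, samples or data. The downside is that no significance claim is made for the supportive variables. If the sponsor already intends to analyse Cl/F on the log scale, one clause settles that part.
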